Children are not able to give informed consent to participate in a study. Therefore, all legal guardians are asked to consent on behalf of the child. Oral and written information about the study, together with general information about participating in a research project from the Danish National Committee on Health Research Ethics is given face-to-face by the PI prior to asking for consent. Information is given in an undisturbed environment at the pediatric ward. The PI is the head of pediatric orthopedic trauma and is very skilled in communication with both parents and injured children.

Unstable or displaced diaphyseal forearm fractures usually do not require emergent treatment, but we strive to treat fractures as soon as possible. In planning, both surgeons and operating personnel need time to prepare for the specific procedure. Therefore, we ask that consent is given the day before surgery at the latest. Parents will in most cases have at least 24 hours to consider enrollment however, there might be factors (e.g. open fracture or neurovascular compromise) that dictate more emergent treatment requiring consent with less consideration time.

If participation is declined the patient will receive standard treatment with TEN, and standard rehabilitation and follow-up after 2 and 6 weeks and 6 months. TEN will be removed approximately 6 months after insertion during a scheduled outpatient operation under general anesthesia.

Follow-up

Outpatient visits are scheduled at 2 and 6 weeks, 3 and 6 months and 1 and 2 years following surgery.

All participants live in the catchment area of our hospital with short transportation time. Information about the time and place for the follow-up examination is sent via the electronic health record (EHR) and physically by mail to the current address registered in the Civil Registration System. Parents are usually very keen to take their children for follow-up appointments making the risk of missing an appointment low. Any participants who miss an appointment will be contacted by phone to reschedule.

Withdrawal

If a participant chooses to discontinue the follow-up examinations for any reason, the date and reason for drop-out is recorded and the latest examination will be carried forward in the analysis. In case of reoperation, the patients continue with their follow-up examinations and they are included in the 2-year analysis. In case of drop-out before the first follow-up visit the participant will be excluded from the

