analysis. The author will record any protocol violations. Participants are only removed from the study if they decline participation.

Surgical technique and post-operative regime

The preoperative investigations are the same as for operations with a conventional metal implant. They consist of clinical history, physical examination and radiographs in anterior-posterior (AP) and mediallateral (ML) plane. All operations will take place at our hospital and will be carried out by one of five experienced orthopedic trauma surgeons. The surgical procedure is almost identical with that of metal ESIN except the exchange to a bioabsorbable implant after dilation of the medullary canal.

The Activa IM-Nail[™] is implanted according to the manufacturer's surgical technique. Operations are performed under general anesthesia together with a peripheral nerve block (PNB) [31]. Prophylactic antibiotics are given in the form of cloxacillin with dose according to the patient's weight. In the case of allergy towards cloxacillin, cefuroxime will be used as an alternative. Patients are in the supine position with the injured arm on a radiolucent arm table. One incision is made over the radial aspect of the distal radius taking care not to harm the dorsal branch of the superficial radial nerve. Another incision is made over the radial aspect of the proximal ulna. The customized instrumentation for the Activa IM-Nail[™] is used. The cortical bone is opened using an awl and an appropriate size dilator is used. The dilator is replaced with the appropriate size bioabsorbable nail under image intensification to the desired depth and the implant is cut flush with the cortical surface. Wounds are closed using absorbable sutures and dressed. The injured arm is put in an above elbow posterior splint. Post-operative radiographs are taken. The patient is discharged when the effect of the PNB has worn of and the child is well, either on the same day or day after surgery. No formalized physiotherapy or rehabilitation is given beside oral and written information on exercises.

Risks, side effects and disadvantages

Based on previous studies using the Activa IM-Nail[™] [7] we predict that the risk of side effects is comparable or less than those seen with metal ESIN.

Infection

Any surgery caries the risk of infection, however previous studies have shown close to no infection risk [3,32] with the ESIN procedure.

Nerve complications

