Studies have shown a 5% risk of nerve injury [32], however all cases had spontaneous recovery of nerve function.

Extra visits to the outpatient clinic

We follow all patients with six visits to the outpatient clinic. This is three more than with standard treatment and might be viewed as a disadvantage.

Radiation

Three extra radiographs are obtained during outpatient visits. A radiograph of an extremity leads to a radiation dose of less than 0.001 mSv and compares to 3 hours of background radiation. Three extra radiographs is far below the threshold of 0.1 mSv.

MRI

Two years after surgery an MRI is performed. We follow a special MRI-protocol without the need for sedation or anesthesia.

Variables

At recruitment baseline data will be collected:

- Demographic data (age, gender, handedness, height and weight)
- Injury data (date and time, left or right arm, location, activity, mechanism, open or closed fracture, diagnosis code, indication for surgery)
- Historical data (metabolic disease, medication, other systemic illness)

After surgery, operative data is collected (date and time of surgery, operative time, closed or open reduction, any complications).

During follow-up in the outpatient clinic data will be collected on:

- Pain (Faces Pain Scale Revised) or VAS according to child's age
- Use of pain medication
- Wound appearance (visible signs of infection)
- Neurovascular status
- Bilateral elbow and forearm range of motion (ROM) measured in degrees by goniometer
- Forearm radiographs in AP and ML planes (Radiographic Union Score)

2 years following surgery MRI findings (absorption of the nail, activity at fracture site, soft-tissue reactions) will be collected.

Outcomes

The primary objective is quantified using the Radiographic Union Scale (RUS) [33] based on degree of callus formation and visibility of fracture line on AP and ML plain radiographs. We define established healing as a RUS of > 9.

Secondary objectives are described as absolute risk of refracture, time to established healing (weeks), pain (Faces Pain Scale – Revised (FPS-R) or visual analogue scale (VAS)), elbow and forearm range of motion (in degrees), visible signs of infection, neurovascular complications and any reoperation. MRI findings (absorption of the nail, activity at fracture site, soft-tissue reactions) after 2 years are described.

The Radiographic Union Score

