To quantify pain in children age 8 and above we will use a visual analogue scale (VAS) (Figure 2). VAS has been extensively investigated in quantifying pain in older children [40,41]. The child is asked to put a mark on the line corresponding to the child's pain at that moment. A mark to the far left equals no pain and a mark to the far right equals worst possible pain. The line is 10 cm long and the child's mark is measured from left to right in cm with one decimal e.g. 3.4 cm equaling a VAS of 3.4. If the child cannot cooperate to using VAS, FPS-R is used instead.

Figure 2 - Visual analogue scale (VAS) for quantifying pain in children age 8 and above.

Bias

We strive to minimize bias in our study. Displaced forearm fractures do not go unnoticed. A strict protocol for referrals for treatment are in place in Denmark. All eligible patients referred to Herlev and Gentofte University Hospital will be asked to participate in the study. We speculate that by enrolling 30 participants the cohort will be representative of the background population. We speculate that these efforts will limit

selection bias. Efforts described in the follow-up section reduce the risk of loss to follow-up. Overall, we find a low risk of bias in our study for the chosen study design and size.

Study size

The surgical procedure for the Activa IM-Nail[™] resembles that of TEN very much and performing surgeons are all experienced traumatologists. All surgeons will be thoroughly introduced to the procedure, the instruments and the implants, thereby minimizing learning curve phenomenon. We predict that 30 participants will be sufficient in establishing the basis for planning a randomized trial.

Statistics

Data will be analyzed using SPSS (SPSS, Chicago, IL, USA). Descriptive statistics will be used to present the patient-related data, number of dropouts, radiological outcome and number of complications (categorical variables). Age and functional outcome (continuous variables) are expected to be expressed as medians with interquartile ranges. Changes in functional outcome between measurements are expected to be analyzed using Friedman test for related non-parametric data. A p-value of <0.05 is regarded as being significant.

Discussion

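### Change in function is tested only with an omnibus Friedman test, so the plan gives no within-child change in degrees, with its uncertainty, between any two visits

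*Combined protocol and SAP*

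**What the plan says.** Functional outcome is a secondary objective (Objectives). It is recorded as "Bilateral elbow and forearm range of motion (ROM) measured in degrees by goniometer" (Variables), so there are several motion variables. The visit schedule has six points: "Outpatient visits are scheduled at 2 and 6 weeks, 3 and 6 months and 1 and 2 years following surgery" (Follow-up).

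The Statistics section describes function with "Age and functional outcome (continuous variables) are expected to be expressed as medians with interquartile ranges". For change it says "Changes in functional outcome between measurements are expected to be analyzed using Friedman test for related non-parametric data", and then "A p-value of <0.05 is regarded as being significant". It names no reference visit, pairwise comparison, multiplicity rule, change estimate or confidence interval. It does not say which visits enter the test or how many tests are run.

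On missing data, when a child discontinues, "the latest examination will be carried forward in the analysis" (Withdrawal). Missed appointments are rescheduled by phone (Follow-up). Only drop-out before the first visit leads to exclusion. Nothing is said about a single visit, or a single motion measurement, that stays missing in a child who remains in follow-up.

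After surgery, "The injured arm is put in an above elbow posterior splint" (Surgical technique and post-operative regime). The duration of splinting is not given, nor whether motion can be measured at 2 weeks.

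**The concern.** The plan's question is how function changes from one measurement to the next. The Friedman test answers a different one: whether the visits, taken together, are compatible with no difference at all. A small p-value has no location, direction or size.

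This matters most late in follow-up. The background section says the implant is fully absorbed over about two years, so stability or loss of motion after the first months is of interest for this device. If motion starts low, a significant six-visit test would look the same whether function then holds or falls.

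The study is also meant to inform a randomised trial: "We predict that 30 participants will be sufficient in establishing the basis for planning a randomized trial". For that purpose a within-child change in degrees with its interval is useful, and an omnibus p-value is not.

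The test also needs a value at every visit from every child. A child with one unfilled intermittent gap would leave it entirely.

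**Working it through.** **Inputs from the protocol.** n = 30 (Study size), k = 6 visits (Follow-up), alpha = 0.05 (Statistics). No effect size, SD, power or precision target is given, so there is no planned figure to reproduce. All deficits, SDs and miss rates below are assumptions.

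**1. What decides the test.** Friedman test on simulated data with independent normal within-child errors, n = 30. A child's overall level does not matter, because ranking is within child. Shifts are in within-child SD.

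| Assumed course | Visits entered | Rejection rate |
|---|---|---|
| No change at any visit | all six | about 5% |
| 2 weeks lower by 1 SD, the rest equal | all six | about 94% |
| 2 weeks lower by 1.5 SD, the rest equal | all six | nearly 100% |
| −2 SD at 2 weeks, −1 SD at 6 weeks, then flat | all six | 100% |
| The same, with a fall of 0.75 SD at 2 years | all six | 100% |
| Flat from 3 months | 3 months to 2 years | about 5% |
| Fall of 0.75 SD at 2 years | 3 months to 2 years | about 72% |

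The fourth and fifth rows are the point: with these early deficits the six-visit p-value cannot separate stable function from late loss. The last two rows show that the later visits do carry that information.

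A smaller early deficit weakens the effect. With an assumed within-child SD of 8 degrees and half the 2-week deficit remaining at 6 weeks, deficits of 5, 8 and 10 degrees give rejection in about 57%, 96% and 99.9% of runs.

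**2. Unfilled intermittent gaps.** If each visit is missed independently with probability m and stays missing, the expected number of complete children is 30 × (1 − m)^6:

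- m = 0.02: 30 × 0.886 = 26.6
- m = 0.05: 30 × 0.735 = 22.1
- m = 0.10: 30 × 0.531 = 15.9

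These figures only illustrate the mechanism. They assume that every gap is intermittent and that rescheduling recovers none.

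**3. Unplanned follow-up testing.** Six visits give 6 × 5 / 2 = 15 pairs. Unadjusted at 0.05, and treating the tests as independent, the chance of at least one false positive is 1 − 0.95^15 = 0.54. For the five consecutive pairs it is 1 − 0.95^5 = 0.23. The comparisons should therefore be few and named in advance.

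**4. Precision available.** The half-width of a normal-theory 95% interval for a paired mean change is t(0.975, 29) × SD / √30 = 2.045 × SD / 5.477. For an assumed SD of change of 10, 15 or 20 degrees it is 3.7, 5.6 or 7.5 degrees. A rank-based interval would differ somewhat, but this shows the order of size.

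**The case against.** Several points on the other side are sound.

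- **Missing visits.** A reader might infer that the test drops every child who misses a visit. The documents do not support that: drop-outs are carried forward and missed appointments are rescheduled. The Follow-up section also expects few missed visits. Only intermittent gaps that stay unfilled are at risk.
- **Descriptive results.** A reader might infer that the plan cannot show when or by how much function changes. Medians with interquartile ranges are planned. If reported by visit, they would show the group course in degrees, and a clear late decline would be visible. What they lack is the change within a child and its uncertainty.
- **The rejection rates are not error rates.** Where motion really is lower at 2 weeks, rejection is correct. The weakness is that the result is uninformative about later change, not that it is false. The protocol nowhere says that p < 0.05 will be read as continuing improvement.
- **Early recovery is assumed.** There are no motion data and no splint duration. If motion is not measured at 2 weeks, that visit may not enter the test. A single test over all six visits is the natural reading, but it is not stated.
- **A mixed model is not a required replacement.** With one residual variance it can mislead if spread narrows over time. Under assumed within-child SDs of 15, 10, 6, 4, 4 and 4 degrees, its interval for 6 months versus 2 years averaged ±4.2 degrees, against ±2.1 for a simple paired interval. Coverage for 2 versus 6 weeks fell to about 80%.

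Function is also a secondary objective in a descriptive pilot. All of this limits the point. None of it supplies the missing contrasts or intervals.

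**Conclusion.** The point holds in limited form. The only planned inference on change in function is an omnibus test, without any contrast, within-child estimate or confidence interval. That follows from the text and needs no assumption.

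The claim that early recovery would decide the result is conditional on low motion at the first visits. With deficits of 2 and 1 SD, the six-visit test rejects in 100% of runs under both late courses. With a 5-degree deficit (SD 8 degrees), it rejects in only about 57%. The loss of children applies solely to unfilled intermittent gaps, and its size is unknown.

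This is a cheap and worthwhile improvement to a secondary analysis. The Friedman test is a valid global test. Healing at 3 months, the refracture rate and the stopping criterion are untouched.

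**What to change.** In Statistics, make the main analysis of change a short prespecified set of paired comparisons for each motion direction: the five pairs of consecutive visits, plus 6 months versus 2 years. Report each as a Hodges-Lehmann median paired difference in degrees with a 95% confidence interval, using all available observed pairs and giving the number of pairs. Either omit p-values or adjust them by Holm within each motion direction. With six comparisons, the smallest p-value is then compared with 0.05 / 6 = 0.0083. The Friedman test may stay as a global test if wished, with the visits entered stated.

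Add a sentence on visits that stay missing in children still in follow-up. With observed pairs, such a child contributes every pair for which both values exist. Since the Withdrawal section carries the last examination forward, say there that the paired comparisons use observed values only.

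The cost is a few sentences, slightly more analysis and several intervals to report. No new data are needed, and the primary outcome does not change.

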Study protocol - Use of the bioabsorbable Activa IM-Nail™ in pediatric diaphyseal forearm fractures: a cohort study of 30 patients Version 3.5 – May 2021 – Protocol ID: H-21004012

Study protocol

Use of the bioabsorbable Activa IM-Nail[™] in pediatric diaphyseal forearm fractures: a cohort study of 30 patients

[name], [name], [name] and [name]

Herlev and Gentofte University Hospital, Copenhagen, Denmark

The Danish Data Protection Agency ID: P-2020-1197 The Danish National Committee On Health Research Ethics ID: H-21004012

Abstract	3
Introduction	4
Background	4
Epidemiology	4
Treatment options	4
Metal Elastic Stable Intramedullary Nailing (ESIN)	5
Hardware removal	5
Bioabsorbable implants	5
Objectives	6
Primary objective	6
Secondary objectives	6
Hypothesis	6
Methods and materials	6
Study design	6
Selection and withdrawal of participants	7
Surgical technique and post-operative regime	9
Risks, side effects and disadvantages	9
Variables	
Outcomes	11
The Radiographic Union Score	11
Faces Pain Scale – Revised (FPS-R)	11
Visual analogue scale	12
Bias	12
Study size	13
Statistics	13
Discussion	13
	40
Ethics and security	
Ethics	
Identification of the implant	
Hospital records Data security	
Data security	14
Publication	15
Perspective	15
Disclosures and economy	15
Literature	16

Abstract

Background

Pediatric diaphyseal forearm fractures are common and one of the most frequent reasons for orthopedic care. Fractures in need of surgery are often treated with metal Elastic Stable Intramedullary Nails (ESIN). Nail removal after 6-12 months is generally advocated. Surgical hardware removal has few complications; however, it is a substantial burden on the child, the family and healthcare economy. Bioabsorbable Intramedullary Nails (BIN) have been developed for the same indications as metal ESIN. The use of bioabsorbable implants would deem hardware removal unnecessary and relieve the child of further surgery and reduce healthcare costs.

Methods

We aim to recruit all children in the catchment area of Herlev and Gentofte University Hospital (Copenhagen, Denmark) with acute unstable diaphyseal forearm fractures. Participants will be operated with BIN and followed consecutively for 2 years with interim analysis of data after 6 months. We will report radiological healing using the Radiographic Union Score (RUS) 3 months after surgery together with any adverse events during follow-up.

Discussion

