Implants made from oriented poly L-lactide-co-glycolide (PLGA) copolymers are strong enough to support fractured bones. The monomers of PLGA are L-lactic acid and glycolic acid, which are part of the normal metabolic chemistry of human cells. PLGA implants undergo a controlled degradation through hydrolysis forming lactic acid and glycolic acid which are absorbed by the cells and metabolized into carbon dioxide and water. The implant retains strength and size for at least eight weeks and over the course of approximately two years the implant will be completely absorbed [28]. Medical grade PLGA implants manufactured by Bioretec Ltd. ([name]) are sterilized with gamma radiation. Gamma radiation also reduces molecular weight of oriented PLGA implants. The reliability and safety of the Activa IM-Nail[™] has been described in the manufacturer's premarket trials and one RCT [7], the implant is FDA and CE approved for the same purpose as in the present study.

Objectives

Primary objective

The primary objective of this study is to evaluate the amount of radiological healing three months after surgery with the Activa IM-Nail[™] for pediatric diaphyseal forearm fractures.

Secondary objectives

The secondary objectives are to report the functional outcome, calculate refracture rate and any other complications up to two years following surgery and to describe MRI findings two years after insertion of Activa IM-Nail™.

Hypothesis

We hypothesize that radiological healing is established three months after surgery with the Activa IM-Nail™.

Methods and materials

Study design

We use a cohort study design [29] conformed to the STROBE Statement [30]. We aim to recruit all children with diaphyseal forearm fractures (cohort) operated with BIN (exposure) and report radiological healing

(outcome). This study design is relevant in reporting radiological healing and calculating absolute risk of adverse events based on the exposure in our cohort.

Selection and withdrawal of participants

Setting

The study will be performed in the Capital Region of Denmark, Europe. Patients in Herlev and Gentofte University Hospital's catchment area (population 700.000 of which 80.000 are children age 3-15) are eligible for recruitment.

Participants

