This study investigates the treatment of pediatric forearm fractures; therefore, this study cannot be conducted in consenting adults. Forearm fractures occur in all age groups and thus it is not possible to select only older children for inclusion. This study is believed to have great positive implications for the participants and successive patients with the same condition.

Participants eligible for recruitment are patients from 2 years of age until physeal closure with an acute traumatic diaphyseal forearm fracture of the radius, ulna or both. Fractures need to be complete (not unicortical or green stick) and displaced more than 50% of bone width or angulated more than 10° in any plane or irreducible or unstable after reduction.

We exclude patients

- with fractures that are well managed conservatively (undisplaced or minimally displaced)
- with previous ipsilateral forearm fracture
- with fractures unsuited for intramedullary nailing (e.g. multifragmentary, metaphyseal or epiphyseal)
- with fractures with ipsilateral wrist or elbow involvement (e.g. Monteggia or Galeazzi variants)
- unable to participate in follow-up
- with existing bone pathology (e.g. tumor, osteogenesis imperfecta, degenerative disease)
- in whom internal fixation is otherwise contraindicated (e.g. active or potential infection)

Recruitment

Recruitment starts May 25th, 2021 and is estimated to take 12 months. Patients may be seen primarily in our Emergency Department (ED) or referred by local clinics or another hospital. Patients with displaced forearm fractures are reviewed daily by the department's trauma surgeons. Any patients eligible for recruitment are referred to the PI for evaluation. Eligible patients are contacted by the PI and invited to a

scheduled visit as soon as possible. The parents are informed of the possibility of bringing an assessor. Parents, and when applicable the child, are informed face-to-face about the project. Parents are given both oral and written information. Patients are recruited at Herlev and Gentofte University Hospital by the principal investigator (PI).

Informed consent

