Operative treatment with metal ESIN is the preferred technique for stabilizing pediatric forearm fractures. Removal of the metal nails is generally advocated in many countries including Denmark. By using BIN, a second operation to remove the nails is avoided.

The hypothesis is that satisfactory fracture healing is accomplished 3 months after operation with BIN. The only previous study on BIN used forearm rotation and not fracture healing as primary outcome [7]. The authors describe that all 15 fractures operated with BIN had healed after 2 years.

The cost of one Activa IM-Nail[™] (\$400) is approximately 4 times higher compared with a traditional TEN (\$100). However the cost of implant removal is approximately \$1900 [7,42] and the extra implant costs are readily balanced out.

Ethics and security

Ethics

The implant is CE approved for the same indications as the use in this study. Permission from the Danish Data Protection Agency is obtained before the inclusion is initiated. The trial will be conducted in accordance with the Declaration of Helsinki of 1996 and principles of good clinical practice.

As with any treatment in the Danish healthcare system all patients are insured and covered by The Patient Compensation Association (Patienterstatningen).

To quantify any unknown side effects or complications an interim analysis of data will be performed 6 months after recruitment of the last patient. An absolute refracture rate of more than 25% is not tolerated and will be a criterion for stopping the study.

In comparison with the standard follow up of pediatric forearm fractures there are 3 additional visits to the out-patient clinic with radiographs of the forearm in AP and ML view. Collectively, the effective dosage is 0.003 mSv - far below 0.1 mSv and is considered insignificant.

Identification of the implant

The traceability of the device is identified by device name, catalogue number (REF) and batch number (LOT).

Hospital records

No access to the patient's EHR regarding the study is made before informed consent to participate is given.

In order to plan and conduct visits, admission and operation we ask that consent is given to access the patient's EHR. We ask permission to retrieve patient-related data and to read entries regarding visits, admission and operation. We ask permission to access radiographs and MRIs.

We ask that access the patient's EHR is given until the conclusion of the project.

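### The 25% refracture stopping limit has no scheduled check until all 30 children have been operated; a short amendment could add one during recruitment

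*Combined protocol and SAP*

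**What the plan says.** The Ethics section (under Ethics and security) schedules one interim analysis: "an interim analysis of data will be performed 6 months after recruitment of the last patient". Its stated purpose is to quantify unknown side effects or complications. The next sentence sets the limit: "An absolute refracture rate of more than 25% is not tolerated and will be a criterion for stopping the study". That sentence gives no time, unit, denominator or responsible role.

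The Abstract (Methods) describes participants as "followed consecutively for 2 years with interim analysis of data after 6 months", without saying from when the six months run. The Recruitment section says: "Recruitment starts May 25th, 2021 and is estimated to take 12 months". Under Informed consent, consent is due by the day before surgery and treatment is to be as early as possible. The Withdrawal section mentions a 2-year analysis. The Statistics section describes no earlier look.

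On what is counted, the Study design section speaks of "calculating absolute risk of adverse events based on the exposure in our cohort", the secondary objectives aim to "calculate refracture rate and any other complications up to two years following surgery", and the Outcomes section says "Secondary objectives are described as absolute risk of refracture". None of these is linked to the 25% limit. Eligibility covers an "acute traumatic diaphyseal forearm fracture of the radius, ulna or both".

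**The concern.** A stopping criterion in a study of an implant would ordinarily be able to halt further implantation. Here the only scheduled interim look is tied to the last recruitment, so it comes when no operation in the study is left to withhold. The sponsor calls a rate above 25% not tolerated, yet the plan names no point during recruitment at which anyone compares the observed rate with that figure. If the rate were that high, every planned child could be operated before the limit was formally applied.

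Smaller gaps make the limit harder to apply when the time comes. It is not stated whether 25% is of children or of bones, who decides, or what stopping means once only follow-up remains.

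**Working it through.** **Inputs from the protocol.** 30 children; recruitment estimated at 12 months; interim 6 months after the last recruitment; limit above 25%. The protocol gives no operating characteristics for the limit, so there is no figure of its own to reproduce.

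**1. Timeline.** If recruitment lasts A months, the interim falls at month A + 6. For A = 6, 12, 18 or 24 that is month 12, 18, 24 or 30. In each case 30 of 30 are operated and 30 − 30 = 0 operations remain. The result does not depend on accrual speed.

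**2. The Abstract's six months.** Read as six months of follow-up, it agrees with the Ethics section, because the last child then reaches the 6-month visit. Counted from the start of recruitment, with even accrual, it would fall when 30 × 6/12 = 15 children are operated, 15 are still to come and none has 6 months of follow-up. The first reading is the more natural.

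**3. What the limit means in counts.** 7/30 = 23.3% and 8/30 = 26.7%, so at least 8 children. If both bones were operated in every child, 15/60 = 25.0% is not above the limit, so at least 16 bones.

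**4. One complete look at 30 children.** P(X ≥ 8) = Σ C(30,k) pᵏ(1−p)³⁰⁻ᵏ for k = 8 to 30:

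| True risk p | 10% | 15% | 25% | 30% | 40% |
|---|---|---|---|---|---|
| P(X ≥ 8) | 0.8% | 7.0% | 48.6% | 71.9% | 95.6% |

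**5. A running check during recruitment (simulation, assumed inputs).** Assumptions: accrual uniform over 12 months; refracture time uniform within a window after surgery; checking starts at the 10th child in the denominator; a crossing counts only before the 30th operation. Approximate chance of crossing the limit, by refracture window:

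| True risk, denominator | 1.5–6 months | 1.5–12 months | 3–12 months | 1.5–24 months |
|---|---|---|---|---|
| 30%, all operated | 40% | 6% | 2% | 0.2% |
| 30%, at least 3 months of follow-up | 71% | 27% | 16% | 3% |
| 40%, all operated | 71% | 18% | 8% | 0.8% |
| 40%, at least 3 months of follow-up | 92% | 49% | 34% | 7% |

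The highest chance of an unnecessary hold across these windows is about 1% at a true risk of 10% and 4% at 15% with all operated children as denominator. With at least 3 months of follow-up it is about 6–7% and 19%.

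**The case against.** The strongest reply is that the 25% sentence is not tied to the interim analysis. Read as a standing criterion it applies throughout, and this is a single-centre study in which the principal investigator recruits every patient and children are seen at 2 and 6 weeks and 3 and 6 months. A reader might infer from the schedule that the limit cannot act at all during recruitment. The protocol does not support that: an earlier stop is possible. What stands is that it is not planned, because no time, denominator or role is given for it.

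A reader might also infer that the Abstract and the Ethics section contradict each other. They do not: the Abstract leaves its starting point open, and its most natural reading agrees with the Ethics section.

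The benefit can fairly be questioned too. Outside the earliest window, a running check would usually not cross the limit before the last operation, even at a true risk of 40%, and it does worse at 30%. Nor do the documents suggest so high a risk: the section on risks predicts side effects no worse than with metal nails, and the device is already approved for this purpose. Finally, the interim analysis does serve the pilot's stated role of preparing a randomised trial. These arguments limit how much protection can be claimed. They do not supply the missing check.

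**Conclusion.** The point holds as a cheap improvement. As scheduled, the sponsor's own limit can spare none of the 30 children the implant. This follows from tying the interim to the last recruitment and from the short interval between consent and surgery, with no assumption about accrual or risk. The 2-year analysis does not change it.

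The size of the gain from an earlier check is not established. A reader might infer that it would reliably protect children. The range of about 0.2% to 71% at a true risk of 30%, and about 1% to 92% at 40%, rules out that claim without knowledge of refracture timing, which the documents do not give. The case for the change is that it makes a rule the sponsor has already written capable of acting, at little cost. The questions of unit, responsible role and the meaning of stopping are secondary clarifications.

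**What to change.** Amend the Ethics section so that the sponsor's existing 25% criterion is also assessed while recruitment is open, at times and on a denominator that the sponsor sets, by a named role. Keep the analysis 6 months after the last recruitment as a safety summary. In the same amendment, state whether the unit is the child or the bone, the follow-up period to which the 25% refers, and what stopping means once only follow-up remains. Give the starting point of the six months in the Abstract.

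The cost is a few sentences and a route for reporting refractures that occur between visits, with no extra patients or visits. The statistical cost is the risk of an unnecessary hold, and the denominator governs it. At a true risk of 15%, restricting to children with at least 3 months of follow-up raises that risk from at most about 4% to about 19%, against 7.0% for a single complete look, but it also detects a true excess more often. The sponsor should weigh that trade-off when choosing the denominator and times.
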